4.3 STUDY PURPOSE

The purpose of this study is to compare OR3O™ Dual Mobility System to a conventional, single-bearing design Total Hip System in subjects who undergo Primary THA to assess the safety and efficacy of the OR3O™ Dual Mobility System. Data collected in this study will be used to support NMPA regulatory approval of OR3O™ Dual Mobility System in China as well as to support and maintain product registration in global markets.

4.4 SAFETY CONSIDERATIONS

4.4.1 Intended Use

The OR3O™ Dual Mobility System is intended for use in Primary and Revision THA in skeletally mature subjects.

4.4.2 Indications

- Advanced degeneration of the hip joint as a result of degenerative, post-traumatic, or rheumatoid arthritis.
- Fracture or avascular necrosis of the femoral head.
- Failure of previous hip surgery: joint reconstruction, internal fixation, arthrodesis, hemiarthroplasty, surface replacement arthroplasty, or total hip replacement.
- All forms of osteoarthritis.
- Patients with hips at risk of dislocation.
- Femoral neck fracture or proximal hip joint fracture.

The OR3O™ Dual Mobility System is intended for single use only. The modular OR3O Dual Mobility Liners and Inserts are to be implanted without bone cement.

Mating components may be indicated for use without bone cement.

CONFIDENTIAL AND PROPRIETARY

This document contains information that is confidential and proprietary to Smith & Nephew PLC and Smith & Nephew, Inc. and is intended for use only by Smith & Nephew and its manufacturer. It shall not be reproduced or copied in whole or in part, nor shall the contents be disclosed by any means without prior written permission from Smith & Nephew, nor shall anyone make any use of it that is contrary to the expressed or implied wishes of Smith & Nephew.

Clinical Protocol	Study Number: OR3O.2019.10 (China)
Prospective, Multi-center, Randomized, Controlled Study to Evaluate the Safety and Efficacy of the OR3O™ Dual Mobility System versus conventional single bearing design Total Hip System in Primary Total Hip Arthroplasty (THA) Procedures	Version: 1.0, 18Aug2020
	Page: 25 of 90

4.4.3 Contraindications

- Do not use OR3O™ Liners with any polyethylene dual mobility insert other than Smith & Nephew OR3O™ XLPE Inserts of matching bearing size.
- Do not use OR3O™ Liners with metal or ceramic femoral heads made from materials such as stainless steel, CoCr, alumina, zirconia toughened alumina, OXINIUM, or OXINIUM DH.
- Conditions that would eliminate or tend to eliminate adequate implant support or prevent the use of an appropriately-sized implant, e.g.:
 - blood supply limitations;
 - insufficient quantity or quality of bone support, e.g., osteoporosis, or metabolic disorders which may impair bone formation, and osteomalacia; and
 - infections or other conditions which may lead to increased bone resorption.
- Mental or neurological conditions which may tend to impair the patient’s ability or willingness to restrict activities putting the affected limb at risk.
- Physical conditions or activities which tend to place extreme loads on implants, e.g., Charcot joints, muscle deficiencies, multiple joint disabilities, etc.
- Skeletal immaturity.
- Skirted femoral heads are contraindicated for use with this device.

5. OBJECTIVE(S)

5.1 PRIMARY OBJECTIVE

The primary objective of this study is to assess safety and efficacy of the OR3O™ Dual Mobility System in Primary THA at 1 year postoperative.

5.2 SECONDARY OBJECTIVES

The secondary objectives of this study are to assess safety and efficacy of the OR3O™ Dual Mobility System and compatible components in Primary THA up to 2 years after surgery.

CONFIDENTIAL AND PROPRIETARY

This document contains information that is confidential and proprietary to Smith & Nephew PLC and Smith & Nephew, Inc. and is intended for use only by Smith & Nephew and its manufacturer. It shall not be reproduced or copied in whole or in part, nor shall the contents be disclosed by any means without prior written permission from Smith & Nephew, nor shall anyone make any use of it that is contrary to the expressed or implied wishes of Smith & Nephew.

Clinical Protocol	Study Number: OR3O.2019.10 (China)
Prospective, Multi-center, Randomized, Controlled Study to Evaluate the Safety and Efficacy of the OR3O™ Dual Mobility System versus conventional single bearing design Total Hip System in Primary Total Hip Arthroplasty (THA) Procedures	Version: 1.0, 18Aug2020
	Page: 26 of 90

5.3 OTHER OBJECTIVES

Other objectives of the study are to assess the hip dislocation percentage and hospital readmission percentage (cumulative) up to 2 years after device implantation.

6. INVESTIGATIONAL PRODUCTS

6.1 IDENTIFICATION

6.1.1 Investigational Product

The OR3O™ Dual Mobility System (liner and insert) is an acetabular system for THA. It is intended for use in Primary and Revision THA in skeletally mature patients.

OR3O™ Dual Mobility System is comprised of a diffusion-hardened, oxidized zirconium (Oxinium™) acetabular liner with a highly polished inner surface of zirconia, a machined locking taper and backside of Zr-2.5Nb alloy, and an insert of highly cross-linked polyethylene (XLPE).

The OR3O™ Liner is assembled into an acetabular shell with a locking taper. The outer diameter of the OR3O™ XLPE Insert articulates within the OR3O™ Liner and features an inner articular surface, which engages with oxidized zirconium (Oxinium™) or CoCr alloy femoral heads of sizes 22mm (for shell sizes 48mm-52mm) and 28mm (for shell sizes 54mm-74mm). Femoral heads are retained within the OR3O™ XLPE Insert by means of a snap fit locking mechanism.

The OR3O™ Dual Mobility System (liner / insert) is combined with existing commercially available S+N acetabular shells and femoral heads, which will be referred to as OR3O™ Dual Mobility Construct within this protocol. The OR3O™ Liner is designed to mate with a dedicated R3™ or REDAPT™ Modular Press-fit acetabular shell with outer diameter sizes of 48mm to 74mm.

Figure 6-1 illustrates the OR3O™ Dual Mobility Construct with an acetabular shell (with optional screws), an Oxinium™ DH Liner, a XLPE Insert and a femoral head.

CONFIDENTIAL AND PROPRIETARY

This document contains information that is confidential and proprietary to Smith & Nephew PLC and Smith & Nephew, Inc. and is intended for use only by Smith & Nephew and its manufacturer. It shall not be reproduced or copied in whole or in part, nor shall the contents be disclosed by any means without prior written permission from Smith & Nephew, nor shall anyone make any use of it that is contrary to the expressed or implied wishes of Smith & Nephew.

Clinical Protocol	Study Number: OR3O.2019.10 (China)
Prospective, Multi-center, Randomized, Controlled Study to Evaluate the Safety and Efficacy of the OR3O™ Dual Mobility System versus conventional single bearing design Total Hip System in Primary Total Hip Arthroplasty (THA) Procedures	Version: 1.0, 18Aug2020
	Page: 27 of 90

Figure 6-1: OR3O™ Dual Mobility Construct

In this study, non-Hydroxyapatite (HA) R3™ Acetabular Shells and Oxinium femoral head will be used in sites in China. The use of screws to secure the acetabular shell is at the discretion of the surgeon.

The OR3O™ Dual Mobility System will be combined with a compatible Smith & Nephew femoral stem.

6.1.2 Comparator Treatment

The comparator treatment in the study is a conventional, single-bearing design Total Hip System comprised of R3™ Acetabular Shell with XLPE liner and a Smith & Nephew Oxinium (Ox) femoral head.

6.2 PRODUCT USE

Each device is packaged with an IFU (Document ID 81104400) to ensure that the device is used properly and for the intended purposes. It is the Investigator’s responsibility to ensure adherence to this IFU as well as Investigator’s Brochure.

6.3 PACKAGING AND LABELING

Packaging and labeling will be prepared to meet China current laws and regulatory requirements. Package integrity and labelling should be verified prior to use of the product.

CONFIDENTIAL AND PROPRIETARY

This document contains information that is confidential and proprietary to Smith & Nephew PLC and Smith & Nephew, Inc. and is intended for use only by Smith & Nephew and its manufacturer. It shall not be reproduced or copied in whole or in part, nor shall the contents be disclosed by any means without prior written permission from Smith & Nephew, nor shall anyone make any use of it that is contrary to the expressed or implied wishes of Smith & Nephew.

Clinical Protocol	Study Number: OR3O.2019.10 (China)
Prospective, Multi-center, Randomized, Controlled Study to Evaluate the Safety and Efficacy of the OR3O™ Dual Mobility System versus conventional single bearing design Total Hip System in Primary Total Hip Arthroplasty (THA) Procedures	Version: 1.0, 18Aug2020
	Page: 28 of 90

6.3.1 Labeling of Investigational Product

In China, commercially available products (acetabular shells and femoral heads) are combined with an investigational product (OR3O™ Dual Mobility System) to form the OR3O™ Dual Mobility Construct. The R3™ Acetabular Shells and Oxinium femoral head to be used in this study are commercial products in China and will be labeled and packed as per the standard commercial packaging.

OR3O™ Dual Mobility liner and insert are investigational products in China. The standard commercial packaging as marketed in the US will be used for these investigational products. Additional labels will be included on the commercial packaging to specify that the product is for investigational use only in order to meet regulatory requirements for use of investigational devices in China.

6.3.2 Comparator Product

The comparator product to be used in this study are commercial products in China and will be labeled and packed as per the standard commercial packaging.

6.4 PRODUCT ACCOUNTABILITY PROCEDURES

No product accountability procedures will be applied for the acetabular shells, femoral heads and femoral stems in all study sites as these are commercially available products in China.

The study includes the use of investigational devices in China and the following product accountability procedures will be applied for OR3O™ Dual Mobility liners and inserts:

The investigational site will maintain an inventory of the investigational product (IP). The Sponsor or its designee will provide a log(s) to facilitate IP inventory control. The log will contain details of receipt, use, returns etc. of IP. All IP accountability logs must be retained in the Investigator Site File (ISF). These records must be available for inspection by the Sponsor, its designees, or by regulatory agencies at any time. IP Management Instructions will be provided by the Sponsor to the site detailing all additional forms that might need completion (e.g. confirmation of receipt) for IP control.

CONFIDENTIAL AND PROPRIETARY

This document contains information that is confidential and proprietary to Smith & Nephew PLC and Smith & Nephew, Inc. and is intended for use only by Smith & Nephew and its manufacturer. It shall not be reproduced or copied in whole or in part, nor shall the contents be disclosed by any means without prior written permission from Smith & Nephew, nor shall anyone make any use of it that is contrary to the expressed or implied wishes of Smith & Nephew.

Clinical Protocol	Study Number: OR3O.2019.10 (China)
Prospective, Multi-center, Randomized, Controlled Study to Evaluate the Safety and Efficacy of the OR3O™ Dual Mobility System versus conventional single bearing design Total Hip System in Primary Total Hip Arthroplasty (THA) Procedures	Version: 1.0, 18Aug2020
	Page: 29 of 90

The Study Monitor will ensure that the procedures and records are in place for the appropriate reconciliation of all IP. As part of monitoring, the Study Monitor will check that site personnel are following the proper procedures for accountability and completing all necessary documentation.

6.5 SURGICAL TECHNIQUE

All study related procedures with the OR3O™ Dual Mobility System must be performed according to the approved surgical technique.

Surgical techniques are available for different OR3O™ Dual Mobility System / acetabular shell combinations. The appropriate surgical technique needs to be followed when using the OR3O™ Dual Mobility System in combination with R3™ Acetabular Shells (Document ID 71381776).

Surgeons selected to participate in this study will be familiar with implanting Dual Mobility Systems and have expertise in the study procedure.

If device replacement/reconditioning is required during the primary surgery, the investigator shall perform device replacement/reconditioning on the subject in accordance with conventional medical device replacement/reconditioning.

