7.6 ENROLLMENT

The site initiation shall be started only after the EC has approved and the clinical trial agreement has signed at each site. Subjects for whom the consent process has been completed and have been implanted with the study product are considered enrolled. Competitive enrollment continues until the completion of enrolled 170 subjects.

If the subject does not have the OR3O™ Dual Mobility System or controlled system implanted after signing an informed consent form, the subject will be considered to be a Screen Failure. Screen Failures will not count into the total number of enrolled subjects.

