7.8 WITHDRAWAL

7.8.1 Withdrawal from Treatment

Subjects may be withdrawn from having the study device implanted at a date close to surgery or during surgery for the following reasons:

- At the discretion of the Investigator due to:
 - A change in treatment being clinically warranted.
 - An adverse event.
 - Any other significant reason identified by the Investigator.

Subjects who provide informed consent but do not receive the study device for any reason will be considered a Screen Failure. Screen Failures will not count into the total number of enrolled subjects.

If at any point during the study, the study device needs to be revised for any reason the following will apply: Intraoperative data from the revision surgery will be collected including implant information used for revision THA. Subjects will terminate the study following revision surgery. Subjects shall be followed by the Investigator according to sites' standard of care in order to monitor the subject's health status and the outcome of the revision. Data collected following the revision surgery will be reported as follow-up data to the adverse event. Data will not be included as study data but presented separately as safety data. Data collected upon the point of revision will be included as study data.

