9.1.3 Operation Visit (Day 0) / Discharge

1. Collect information on any changes in subject general health and the use of concomitant medications. Update medical history as necessary.
2. Perform surgery and collect intraoperative data on source documents. This includes but is not limited to the following information:
 - Implant product – study arm or controlled arm
 - Implant data
 - Surgical data e.g. duration, surgical approach
 - AEs, Device Deficiencies

Any subject who signs an ICF but fails to be implanted with the study device for any reason is considered to be a Screen Failure.
3. At time of discharge, collect discharge data on source documents. This includes but is not limited to the following information:
 - Discharge Date
 - Mobility Status
 - Medication at discharge
 - AEs, Device Deficiencies
4. Based on standard of care at the study site, the investigator will decide whether the radiographic assessment will be performed prior to discharge or at the 6 weeks follow-up visit. Radiographic images are to be collected in anteroposterior (AP) and lateral view in supine position. Investigator to review the images and radiographic report, as well as record data in the subject's medical record.
5. Instruct the subject on follow-up procedures, including returning to the site for the follow-up visit in 6 weeks (42 days (- 7 days / +14 days) from the date of surgery).
6. Transcribe data to the eCRF.

CONFIDENTIAL AND PROPRIETARY

This document contains information that is confidential and proprietary to Smith & Nephew PLC and Smith & Nephew, Inc. and is intended for use only by Smith & Nephew and its manufacturer. It shall not be reproduced or copied in whole or in part, nor shall the contents be disclosed by any means without prior written permission from Smith & Nephew, nor shall anyone make any use of it that is contrary to the expressed or implied wishes of Smith & Nephew.

Clinical Protocol	Study Number: OR3O.2019.10 (China)
Prospective, Multi-center, Randomized, Controlled Study to Evaluate the Safety and Efficacy of the OR3O™ Dual Mobility System versus conventional single bearing design Total Hip System in Primary Total Hip Arthroplasty (THA) Procedures	Version: 1.0, 18Aug2020
	Page: 46 of 90

9.1.4 Follow-Up visit at 6 weeks post-surgery (42 - 7 days / + 14 days from the date of surgery)

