7.2 Analysis Populations

The following section details the analysis populations:

TMP-CD-30-01 Statistical Analysis Plan - Revision B; SOP-CD-30 Statistical Analysis

CONFIDENTIAL AND PROPRIETARY

This document contains information that is confidential and proprietary to Smith & Nephew PLC and Smith & Nephew, Inc. and is intended for use only by Smith+Nephew and its manufacturer. It shall not be reproduced or copied in whole or in part, nor shall the contents be disclosed by any means without prior written permission from Smith+Nephew, nor shall anyone make any use of it that is contrary to the expressed or implied wishes of Smith+Nephew.

Statistical Analysis Plan

A Prospective, Multi-center, Randomized, Controlled Study to Evaluate theVersion: 2.0,Safety and Efficacy of the OR3O[™] Dual Mobility System versus conventional29-Feb-2024single bearing design Total Hip System in Primary Total Hip Arthroplasty (THA)Page: 13 of 27ProceduresProcedures

Number: OR3O.2019.10 ST: 1100 Version: 2.0, 29-Feb-2024 Page: 13 of 27

Safety (SAF) Population: This is defined as all hips who have been implanted with the OR3O[™] Dual Mobility System or controlled system. The SAF population will be based on the device that is implanted into the hip and not the one the hip is randomized to (if different).

Full Analysis Set (FAS) Population: This is defined according to the basic principle of Intent-to-Treat (ITT) principle i.e., all implanted hips with at least one postoperative effectiveness, HRQoL or performance will be included in FAS Population.

Per-Protocol (PP) Population: The PP population is the subset of hips in the FAS population who do not have major protocol deviations and who satisfied all enrollment eligibility criteria. Criteria that can be regarded as major deviations will be formally classified on a case-by-case basis prior to the final study database lock.

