7.13 Analysis of Safety Endpoints

The following summaries will be performed on the safety endpoints:

• The number of adverse events will be reported both overall and by seriousness, relationship to study device and/or study procedure and expectedness.

CONFIDENTIAL AND PROPRIETARY

This document contains information that is confidential and proprietary to Smith & Nephew PLC and Smith & Nephew, Inc. and is intended for use only by Smith+Nephew and its manufacturer. It shall not be reproduced or copied in whole or in part, nor shall the contents be disclosed by any means without prior written permission from Smith+Nephew, nor shall anyone make any use of it that is contrary to the expressed or implied wishes of Smith+Nephew.

Statistical Analysis Plan

A Prospective, Multi-center, Randomized, Controlled Study to Evaluate theVersion: 2.0,Safety and Efficacy of the OR3O[™] Dual Mobility System versus conventional29-Feb-2024single bearing design Total Hip System in Primary Total Hip Arthroplasty (THA)Page: 26 of 27ProceduresProcedures

Number: OR3O.2019.10 ST: 1100 Version: 2.0, 29-Feb-2024 Page: 26 of 27

- The number of subjects experiencing adverse events will be summarised both overall and by seriousness, relationship to study device and/or study procedure and expectedness.
- An overall AE summary table that will summarize as number (n) and percentages (%), the overall incidence according to subjects with at least one AE; subjects with at least one AE by worst severity (mild, moderate, or severe); subjects with at least one AE by worst outcome (resolved, ongoing/unresolved, or death); subjects with an AE that led to study discontinuation and; subjects with at least one AE by worse relatedness to device. Other events such as SAEs, ADEs, SADEs or ASADEs, USADEs will also be similarly summarized using number (n) and percentages (%).
- Incidence of device- or procedure-related re-interventions that occur on-study will be summarized as number (n) and percentages as well as by type.
- Device deficiencies that occur on-study will be listed.

All safety endpoints will be summarized using the SAF analysis population.

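### When an OR3O attempt is abandoned in theatre and the single-bearing system is implanted, an intraoperative event leaves the OR3O column of the safety tables on either reading of the enrolment rules

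*Protocol*

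**What the plan says.** Protocol 7.8.1 provides for giving up the assigned device in theatre: "Subjects may be withdrawn from having the study device implanted at a date close to surgery or during surgery for the following reasons". The reasons listed include an adverse event. Protocol 6.5 adds: "If device replacement/reconditioning is required during the primary surgery, the investigator shall perform device replacement/reconditioning on the subject". It does not say what replaces what.

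Two rules then decide whether such a subject is in the study.

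- Protocol 7.6 sets the Screen Failure condition as "If the subject does not have the OR3O™ Dual Mobility System or controlled system implanted after signing an informed consent form". A subject who receives either system does not meet it. The same section counts as enrolled those who have consented and "have been implanted with the study product are considered enrolled".
- Protocol 7.8.1 says: "Subjects who provide informed consent but do not receive the study device for any reason will be considered a Screen Failure". Protocol 9.1.3 repeats this at the operation visit: "Any subject who signs an ICF but fails to be implanted with the study device for any reason is considered to be a Screen Failure". Neither section defines study device. The text under the flowchart in Protocol 8.1 names the study device and the controlled device as two different things.

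For hips that are in, SAP 7.2 states: "The SAF population will be based on the device that is implanted into the hip and not the one the hip is randomized to". The same sentence allows for the two being different. SAP 7.13 adds: "All safety endpoints will be summarized using the SAF analysis population". SAP 5.7 includes intraoperative adverse events among the safety endpoints. No sentence says how to attribute an event that arises from a device that was tried and then removed in the same operation.

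**The concern.** Implantation is the step at which a new liner and insert can fail for mechanical or handling reasons, and harm at that step belongs to the device being inserted. A table column defined by what remains in the hip at closure answers a different question: what happened to hips that ended up with OR3O. If an OR3O attempt fails and the single-bearing system goes in, the harm of the attempt is credited either to the comparator or to nobody.

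Safety is part of the primary objective (Protocol 5.1, SAP 5.1). SAP 7.10 and 7.15 drop statistical testing after early termination and rely on descriptive summaries, so the counts in each column are what a reader will use. With fewer hips than planned, one misplaced event weighs more.

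**Working it through.** The plan states no figure on this point, so the check is mainly a trace through the text.

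**Step 1. Can the hip arise?** Protocol 7.8.1 allows the assigned device to be dropped during surgery, and SAP 7.2 provides for an implanted device that differs from the randomised one. So both documents anticipate the situation. Completing the operation with the single-bearing liner is an inference. It is plausible because both arms use the R3 shell (Protocol 2 and 6.1.2).

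**Step 2. Is the hip in the study?** This depends on what study device means in 7.8.1 and 9.1.3.

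| Meaning of study device | Hip randomised to OR3O, closed with control | Consequence elsewhere |
|---|---|---|
| Either system | Enrolled, as in 7.6 | Consistent with 7.6 and with SAP 7.2 |
| The assigned device | Screen Failure | No mismatched hip is enrolled, so the mismatch clause in SAP 7.2 has nothing to act on |
| OR3O only | Screen Failure | Every correctly treated control subject is also a Screen Failure, so 170 cannot be enrolled in two arms |

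The first meaning is the only one under which both documents work. The others remain possible on the wording.

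**Step 3. Where does the event go?** If the hip is enrolled, SAP 7.2 makes it a control hip and SAP 7.13 tabulates its events there. If it is a Screen Failure, it is not enrolled. Adverse events are collected from enrolment (Protocol 8.4.4, SAP 5.7), so the event belongs to neither column.

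**Step 4. What one event does to the table.** The only input from the plan is 85 per arm (Protocol 11.1: 76/0.90 = 84.4, rounded up to 85). The number of switches, k, is an assumption, because the documents give none. Let k hips randomised to OR3O be switched, each with one intraoperative event, with no other events and no replacement of Screen Failures.

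- By randomised arm: k/85 versus 0/85
- Enrolled, by final implant: 0/(85 − k) versus k/(85 + k)
- Screen Failure: 0/(85 − k) versus 0/85

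| k | By randomised arm (OR3O v control) | By final implant | Screen Failure |
|---|---|---|---|
| 1 | 1/85 = 1.18% v 0% | 0/84 v 1/86 = 1.16% | 0/84 v 0/85 |
| 2 | 2/85 = 2.35% v 0% | 0/83 v 2/87 = 2.30% | 0/83 v 0/85 |
| 4 | 4/85 = 4.71% v 0% | 0/81 v 4/89 = 4.49% | 0/81 v 0/85 |

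In this example the difference reverses sign on one reading and vanishes on the other. A switch without an event moves no event; it only moves a hip between denominators or drops it.

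**The case against.** The strongest reply is that crossover is not what Protocol 6.5 describes. Tables 24-1 and 24-2 list 13 OR3O liners and 14 inserts, so exchange for another OR3O component fits the sentence equally well and leaves the hip in the OR3O group. That stands: 6.5 cannot carry the point alone. The point rests on 7.8.1 and on the mismatch clause in SAP 7.2.

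Second, it can be argued that an OR3O liner seated and then removed was still implanted. The safety set is defined as hips implanted with either system, so the wording leaves some room. But the grouping sentence speaks of one device per hip, and the final implant is the natural reading. If the other was meant, the SAP has to say so.

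Third, the cause would not be lost from the data. Protocol 12.3 requires product details for adverse device effects and deficiencies, and SAP 7.13 splits events by relationship and lists device deficiencies. This helps anyone reading individual cases. It does not repair the incidence tables: Protocol 12.1.2 includes the comparator in its definition of adverse device effect, so a device-related event in the control column reads as a control-device event.

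Fourth, grouping by implanted device is a common choice for safety, and it is sensible for postoperative events, which arise on the bearing actually present. That stands, and the fix keeps it.

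A reader might go further and infer that OR3O failures will be moved into control in numbers that distort the whole safety comparison and the OR3O survival curve. The documents do not support that. They give no switching rate and no event rate. The grouping rule also works in both directions, so a failed control attempt finished with OR3O would count under OR3O. For survivorship, the opening of SAP 7 assigns secondary endpoints other than radiographic ones to the FAS while SAP 7.11 assigns them to the SAF, so the set is itself unsettled.

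**Conclusion.** The point holds as a gap in attribution combined with a contradiction on enrolment status. For a hip randomised to OR3O that leaves surgery with the single-bearing system, an intraoperative event caused by the OR3O attempt is tabulated under control (7.6 with SAP 7.2 and 7.13) or in neither arm (7.8.1 and 9.1.3 read as Screen Failure). Both routes take it out of the OR3O column, and no planned safety table by randomised arm would restore it.

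For that hip the direction is clear. The size over the trial is unknown and none is claimed; the figures above show only what each event does at an assumed 85 per arm. The conclusion assumes that at least one such switch with an intraoperative event occurs, and that implanted means the device in place at closure. It should be settled before the tables are produced, but it does not by itself undermine the trial.

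**What to change.** 1. In SAP 7.2 and 7.13, keep the as-implanted safety set for postoperative events. State that an intraoperative event is attributed to the device in use or being attempted at its onset, with all hips in which that device was attempted as the denominator. A switched hip may then be in both intraoperative denominators, but each event is counted once.
2. Add a supplementary safety summary by randomised arm covering all randomised subjects who entered surgery. List each intraoperative switch with its reason, by randomised arm.
3. Define study device, and reconcile Protocol 7.6 with 7.8.1 and 9.1.3 so that a switched hip and its events are not dropped as a Screen Failure.

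SAP 2 already provides for an addendum or an amended SAP, which can carry the first two items. The cost is one extra table and one derived flag. The flag can be built from the operative data (Protocol 9.1.3 records the implant product, implant data, adverse events and deficiencies) and from the OR3O liner and insert log (Protocol 6.4). Confirm that the operative form records a device attempted and removed, not just the final implant. The change concerns definitions and tabulation only and touches no surgical decision.
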